5 SAMPLE SIZE AND POWER

Approximately 500 subjects with type 1 diabetes will participate in this trial. The sample size estimation is based on primary objective - to demonstrate that immunogenicity as assessed by TEAR rate with MYL-1601D is equivalent to that of NovoLog® during 24-week treatment. The 80% power will be achieved with 250 subjects per treatment arm to demonstrate that 90% confidence interval of treatment difference (MYL-1601D minus NovoLog®) is within prespecified \pm margin (Table 2 of the SAP) (Chow SC et al, 2002; Chow S-C et al 2003). The pre-specified equivalent margin is dependent on the final rate of NovoLog® TEAR rate. No replacement of subject will be performed if subject discontinued prematurely from the study.

Table 2: Margins and 95% CIs with different reference TEAR event rates in 500 subjects

Event Rate for Reference Product	Estimated 95% CI for the Event Rate (n=250)	Margin	Type I error 2 one-sided alpha	Power	Total N
5%	(2%,8%)	5.7%	0.05	80%	500
10%	(6%,14%)	7.9%	0.05	80%	500
15%	(11%,19%)	9.3%	0.05	80%	500
20%	(15%,25%)	10.5%	0.05	80%	500
25%	(20%,30%)	11.3%	0.05	80%	500
30%	(24%,36%)	12.0%	0.05	80%	500
35%	(29%,41%)	12.5%	0.05	80%	500
40%	(34%,46%)	12.8%	0.05	80%	500
45%	(39%,51%)	13.0%	0.05	80%	500
50%	(44%,56%)	13.1%	0.05	80%	500
55%	(49%,61%)	13.0%	0.05	80%	500
60%	(54%,66%)	12.8%	0.05	80%	500

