6.2 ITT analysis set

The ITT analysis set includes all randomized subjects without being in the site with GCP violation (including subjects who receive incorrect treatment, do not complete the study or do not comply with the protocol or used prohibited medication, randomized but do not take any study drug). The subjects who are in the site with GCP violation will be excluded from ITT analysis set.

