8.7.1 Analysis methods

Definition of Primary Endpoints

The TEAR rate during 24-week treatment period is the primary endpoint for this study. TEAR is defined as either one of the following:

- 1) Subjects who are ADA negative at baseline and become positive at any timepoint post baseline.
- 2) Subjects who are ADA positive at baseline and demonstrate 4-fold increase in titer values at any timepoint post baseline visit.

Although differences in TEAR rate is the primary endpoint for the study from a statistical perspective, given that immunogenicity is not a standard endpoint in clinical trials, this difference, even if significant, will not be assessed in isolation but will be part of totality of evidence including changes in HbA1c, FBG, insulin dose, neutralizing antibodies and injection site reactions to ensure that changes in TEAR rate, if any, are clinically correlated and meaningful.

Statistical Methodology for Primary Endpoint

The 90% confidence interval of the treatment difference (MYL-1601D minus NovoLog®) in the TEAR rate will be established using the Wald confidence limit method with multiple imputation (Section 8.7.2.1). The MYL-1601D TEAR rate will be declared equivalent to that of NovoLog® during the 24-week treatment period if the 90% confidence interval of the treatment difference in TEAR rate is within the pre-specified margin as displayed in Table 2 of the study SAP, as suggested by Chow et al. (2002; 2003). For specific reference drug rate-based margin calculation, please refer to the SAS example code in Section 10 (Appendices – SAS Example Codes).

The primary analysis will be based on the ITT population. In addition, all post-discontinuation and rescue data will be included in the analysis.

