If the subject was ADA positive at baseline, then the imputed titer values will be used. The subject will be considered TEAR positive if the ADA titer at any post-baseline visit was $\geq 4\times$ the baseline titer. If none of the post-baseline titer values reached 4 times the baseline titer, then the subject will be classified as TEAR negative.

For each imputation, the proportion of responders, along with standard errors, will be estimated for each treatment group, and the estimate and standard error of the risk difference will be computed. These values will be combined across imputations using PROC MIANALYZE. Subsequently, the 90% confidence interval for the risk difference will be computed using the Wald confidence limit method.

An equivalence margin will be established as a function of the TEAR rate among the Novolog subjects. Under the null hypothesis of equivalence (i.e., $H_0: p_M = p_N$), the margin can be obtained as a function of the TEAR rate in the Novolog group using the following expression (Chow S-C et al., 2003, p. 91).

$$\delta = (z_\alpha + z_\beta) \sqrt{\frac{2p_N(1 - p_N)}{n_N}}$$

Selected values for δ are provided in Table 2 of Section 5 above. If the margin falls within the 90% confidence interval for the risk difference, then equivalence of MYL1601-D and Novolog will be declared.

These steps can be executed using code similar to the following:

```
proc freq data=simdata ;
title "90% Wald confidence interval";
by _imputation_;
ods output riskdiffcol2=rdiff1;
table group*resp / riskdiff (CL=WALD column=2) alpha=0.1;
weight count;
run;

data rdiff1; set rdiff1;
keep _imputation_ row risk ase lowercl uppercl;
if row='Difference';
run;

proc mianalyze data=rdiff1;
modeleffects risk;
stderr ase;
ods output ParameterEstimates=mirisk1;
run;

ods listing;
data parms1;
set mirisk1;
lowercl = estimate - (1.645*stderr);
uppercl = estimate + (1.645*stderr) ;
run;
proc print data=parms1;
var estimate stderr lowercl uppercl;
run;
```

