10.2 Tipping Point Analysis

The tipping point analysis will create a type of figure called a heat map. It will not impute data at the subject level, but rather will be based on the observed total counts of TEAR status and number of missing values per group.

The steps are summarised below:

For purposes of the code below, set

```
Nm = Total # of subjects randomized to MYL-1601D group
Nn = Total # of subjects randomized to Novolog group
Mm = # of subjects missing TEAR status in MYL-1601D
group
Mn = # of subjects missing TEAR status in Novolog group
TEARm = # of subjects in MYL-1601D group who are TEAR
positive
TEARn = # of subjects in Novolog group who are TEAR
positive
```

Then run code similar to the following. The code below assumes that the above variables have been created as global variables.

```
%macro heat;

data heatmap;
do i = 0 to &mn;
  do j = 0 to &mm;
    y = &tearn + i;
    x = &tearm + j;
    pn = y/&nn;
    pm = x/&nm;
    riskdiff = pm - pn;
    margin = (quantile('NORMAL',0.95) +
    quantile('NORMAL',0.90))*
    sqrt(2*pn*(1-pn)/&nn);
    output;
  end;
end;
run;

%do i = 0 %to &mn;
  %do j = 0 %to &mm;

    data imputed;
    length group $8;
    group="NOVOLOG";
    status=1;
    count=%eval(&tearn+&i);
    output;
    status=0;
    count=%eval(&nn - (&tearn+&i));
    output;
```

```

group="MYL-1601D";
status=1;
count=%eval(&tearm+&j);
output;
status=0;
count=%eval(&nm - (&tearm+&j));
output;
run;

ods exclude all;
proc freq data=imputed;
table group * status / riskdiff (cl=WALD column=2)
alpha=0.1;
weight count;
ods output riskdiffcol2=rdiff1;
run;
ods exclude none;
data ci;
set rdiff1 (where=(row="Difference"));
y = &tearn + &i;
x = &tearm + &j;
run;

data heatmap;
merge heatmap
ci (keep=x y risk ase lowercl uppercl)
;
by x y;
length color $8 digits $16 a1-a6 asterisk $1;
if -0.0000001 <riskdiff < 0.0000001 then do;
red=255;
green=255;
blue=255;
end;
else if riskdiff > 0 then do;
if riskdiff >= 0.16 then do;
red = round(484 - (1435*riskdiff));
green = 0;
blue = 0;
end;
else do;
red = 254;
green = round(255/(1+exp(-32.96*(0.1149-
abs(riskdiff)))));
blue = round(255/(1+exp(-21.58*(0.0793-
abs(riskdiff)))));

```

```

        end;
    else if . < riskdiff < 0 then do;
        red = round(255/ (1+exp(-18.51*(0.1108-
abs(riskdiff)))));
        green = round(255/ (1+exp(-27.85*(0.1699-
abs(riskdiff)))));
        blue = round(255/ (1+exp(-20.10*(0.1024-
abs(riskdiff)))));
    end;

    digits = "0123456789ABCDEF";

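### The margin formula printed in SAP 8.7.2.1 gives equivalence margins 15% tighter than SAP Table 2 and the SAP 10.2 code, and neither formula nor code fixes n at the planned 250

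*SAP*

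**What the plan says.** The margin appears in three places in the SAP.

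- **Section 5, Table 2** (identical to protocol Table 5) lists margins for reference rates from 5% to 60% in 5-point steps, for two one-sided tests at 0.05, 80% power and 500 subjects. The text adds: "The pre-specified equivalent margin is dependent on the final rate of NovoLog® TEAR rate".
- **Section 8.7.2.1**, the primary analysis, states that "the margin can be obtained as a function of the TEAR rate in the Novolog group using the following expression" and prints δ = (z_α + z_β)√(2p_N(1 − p_N)/n_N). It then says that selected values "are provided in Table 2 of Section 5 above".
- **Section 10.2**, the tipping-point code, computes the margin as the sum of the 0.95 normal quantile and "quantile('NORMAL',0.90"), multiplied by "sqrt(2*pn*(1-pn)/&nn"). The count is defined as "Nn = Total # of subjects randomized to Novolog group".

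Section 8.7.1 ties the decision to Table 2 and adds: "For specific reference drug rate-based margin calculation, please refer to the SAS example code in Section 10". Section 6.2, as revised in SAP version 3.0, says: "The subjects who are in the site with GCP violation will be excluded from ITT analysis set". The SAP thus has a Randomized set and a smaller ITT set, and the ITT set carries the primary analysis.

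**The concern.** The margin is the pass/fail threshold for the primary endpoint. At the stated 80% power, z_β is the 0.80 normal quantile, whereas the code uses the 0.90 quantile. The formula and the code therefore cannot both generate Table 2, although 8.7.2.1 presents the table as values of its formula.

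The table alone does not settle the matter. The margin depends on the final NovoLog rate, and a multiply imputed rate will rarely fall on a 5-point row. A formula or code has to supply the margin between rows, and the one printed in the primary-analysis section is the one that disagrees.

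The divisor is also open. Table 2 rests on 250 per arm, 8.7.2.1 gives n_N no value, and the code uses the number randomized. After the site exclusion it is unclear whether the randomized or the ITT count should enter the margin for the ITT decision.

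**Working it through.** **Inputs.** One-sided α = 0.05, z = 1.645 (SAP Table 2). Power 80%, so β = 0.20, z_β = 0.842 and z_(β/2) = 1.282. n = 250 per arm and the 12 tabled margins (SAP Section 5). True difference zero (SAP 8.7.2.1).

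**Reproducing Table 2.** Use δ = k√(2p(1 − p)/250) with

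- k = 1.645 + 1.282 = 2.926 (z_(β/2), as in the code)
- k = 1.645 + 0.842 = 2.486 (z_β, as printed)

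For example, at p = 30%, √(2 × 0.30 × 0.70/250) = 0.04099. Then 2.926 × 0.04099 = 11.99% and 2.486 × 0.04099 = 10.19%.

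| Reference rate | Table 2 | k = 2.926 | k = 2.486 |
|---|---|---|---|
| 5% | 5.7% | 5.70% | 4.85% |
| 10% | 7.9% | 7.85% | 6.67% |
| 15% | 9.3% | 9.35% | 7.94% |
| 20% | 10.5% | 10.47% | 8.90% |
| 25% | 11.3% | 11.33% | 9.63% |
| 30% | 12.0% | 11.99% | 10.19% |
| 35% | 12.5% | 12.48% | 10.61% |
| 40% | 12.8% | 12.82% | 10.90% |
| 45% | 13.0% | 13.02% | 11.06% |
| 50% | 13.1% | 13.09% | 11.12% |
| 55% | 13.0% | 13.02% | 11.06% |
| 60% | 12.8% | 12.82% | 10.90% |

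The third column matches every row to rounding and the fourth matches none. The ratio is 2.486/2.926 = 0.850 throughout. Between rows, at 22.5%, the two margins are 10.93% and 9.29%.

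**Power at equal rates, 250 per arm.** Power is 2Φ(δ/SE − 1.645) − 1. With k = 2.926 this is 2Φ(1.282) − 1 = 0.80. With k = 2.486 it is 2Φ(0.842) − 1 = 0.60. Exact binomial enumeration, with the 90% Wald interval and δ taken from the observed NovoLog rate, gives 0.797–0.805 and 0.601–0.606 for true rates of 10–50%.

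**Effect on the verdict.** MYL-1601D counts for which the 90% Wald interval lies inside ±δ, with 250 per arm and complete data:

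| NovoLog positives | k = 2.926 | k = 2.486 | Opposite verdicts |
|---|---|---|---|
| 50 (20%) | 38–60 | 42–57 | 38–41, 58–60 |
| 75 (30%) | 62–87 | 67–83 | 62–66, 84–87 |
| 125 (50%) | 111–139 | 116–134 | 111–115, 135–139 |

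The 42 in the first row is a boundary case. It becomes 43 if 1.645 is used rounded, as in the code in SAP 8.7.2.1.

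**Effect of the divisor.** The margin scales as √(250/n). The documents do not give the excluded site's size, so the n values below are assumptions. The margin is at a 30% reference rate. Power is for δ held at its n = 250 value with n analysed per arm, 2Φ(2.926√(n/250) − 1.645) − 1.

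| n | Code's margin | Relative change | Power with δ held at n = 250 |
|---|---|---|---|
| 245 | 12.1% | +1.0% | 79% |
| 240 | 12.2% | +2.1% | 78% |
| 225 | 12.6% | +5.4% | 74% |
| 260 | 11.8% | −1.9% | not needed |

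**The case against.** The best reply is that the printed expression is not the operative rule. SAP 8.7.1 and protocol 7.2.2 and 7.2.3 refer to the tabled margins. SAP 8.7.1 sends the reader to the Section 10 code for a specific rate, and both tables and the code agree on 2.926. SAP 8.7.2.1 gives β no number, and the formula matches the table if β is read as 0.10. On this view a subscript is missing its /2.

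Much of that is fair: the intended margin is almost certainly the tabled one. But 80% is the only power the plan states, so β = 0.20 is the plain reading. Nothing says that the code prevails over the primary-analysis text, and the code line cited sits in a tipping-point macro. An analyst who follows 8.7.2.1 for a rate between rows gets the tighter margin.

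On n, the subscript N clearly denotes the NovoLog group, so n_N reads naturally as a NovoLog count, and the effect is small. At about a 30% reference rate, computing δ from the actual count instead of 250 leaves the accepted range unchanged at 245 per arm. It moves each end by one subject at 240, and by one or two at 225. That makes the divisor a secondary point. It does not settle which NovoLog count is meant, because version 3.0 makes the randomized and ITT counts differ. Dropouts do not add to the problem, since protocol 7.1 keeps them in the primary analysis through imputation.

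**Conclusion.** The concern holds and must be fixed before unblinding. With β = 0.20 and n = 250, the expression in SAP 8.7.2.1 contradicts SAP Table 2, protocol Table 5 and the SAP 10.2 code. It gives margins 15% tighter and 60% power instead of 80%, and it reverses the primary conclusion in bands of three to five MYL-1601D subjects at each end of the acceptance range for reference rates of 20%, 30% and 50%. The tabled margins are right for the stated power; the printed formula is wrong.

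That Table 2 uses z_(β/2) is inferred from the match in all 12 rows and from the code, because the table does not state its formula. The verdict bands assume 250 per arm and complete data. The open divisor is a real but minor gap, worth about 1% to 5% of the margin in relative terms if 5 to 25 NovoLog subjects are lost from the count, which is an assumed range.

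**What to change.** Before unblinding:

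1. In SAP 8.7.2.1, print δ = (z_0.05 + z_0.10)√(2p_N(1 − p_N)/250), and state that the second term is z_(β/2) with β = 0.20 and that n is fixed at the planned 250 per arm.
2. In the margin line of SAP 10.2, replace &nn by 250.
3. State that this formula gives δ for reference rates between the rows of Table 2, and that it applies unchanged to the ITT, Randomized-set, PP, observed-case and heat-map analyses.

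This changes one formula and one code line and leaves SAP Table 2 and protocol Table 5 as they are. If fewer than 250 NovoLog subjects are analysed, the margin is slightly less favourable than the code's present one. Power at equal rates is then about 79% with 245 per arm, 78% with 240 and 74% with 225.

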7.2.3 Primary Analysis for Primary Endpoints

Equivalence of TEAR rate will be established if 90% confidence interval of treatment difference (MYL-1601D minus NovoLog®) is within \pm margin indicated in Table 5. The pre-specified equivalence margin is based on the final NovoLog® TEAR rate. The primary analysis will be performed on the intent to treat (ITT) analysis set.

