8.7.2.1 Primary efficacy analysis

The primary efficacy analysis will be a test of equivalence for the MYL-1601D and NovoLog® groups in the TEAR rate at Week 24. The null hypothesis is non-equivalence, expressed by

$$H_0: |p_M - p_N| \geq \delta, \delta > 0$$

where p_M and p_N are the (true) proportions of subjects with TEAR in the MYL-1601D and NovoLog[®] groups, respectively, and δ is the equivalence margin. The null will be rejected in favor of equivalence if the 90% confidence interval of the treatment difference is within the range $(-\delta, \delta)$. The confidence interval as defined by Chow and Shao (2002) is constructed as

$$CI_{2\alpha} = [\hat{p}_M - \hat{p}_N - t_\alpha \hat{\sigma}, \hat{p}_M - \hat{p}_N + t_\alpha \hat{\sigma}]$$

where \hat{p}_j is the estimate of the TEAR rate p_j in each treatment group, $j \in \{M, N\}$, $\hat{\sigma}$ is the sample estimate of the standard error of the mean, and t_α the 0.05 quantile of the t distribution with $(N - 2)$ degrees of freedom with N being the pooled number of subjects in the analysis. That is, H_0 will be rejected if neither $-\delta$ nor δ is contained within the 90% confidence interval.

To minimize any bias due to missing data, the primary efficacy analysis will use multiple imputation to fill in missing ADA values. Multiple imputation (MI) will be applied to two measured variables: ADA binary response (positive/negative) and ADA continuous titer values. Multiple imputation will be done for each variable separately, then the two sets of imputed datasets will be merged in order to generate the imputed TEAR status. For subjects who are ADA negative at baseline, post-baseline missing values will be imputed using the binary response values obtained from logistic regression MI. Missing post-baseline values for subjects who are ADA positive at baseline will be derived from the continuous MI model. The primary efficacy analysis is based on the Week 24 (Visit 15) value. Subjects who discontinue treatment prematurely will be classified based on whether ADA values were obtained for the visits after treatment discontinuation (retrieved dropouts) or not.

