8.7.2.3 Tipping point analysis

A tipping point analysis will be used to estimate the point at which the equivalence boundary is crossed and the results fail to reject non-equivalence; that is, where

$$|\hat{p}_M - \hat{p}_N| \geq \delta, \delta > 0$$

The tipping point analysis will consider all possible counts of TEAR positive subjects that could result if TEAR status could be observed for each missing value. This will range from all missing values being imputed as positive to all missing values imputed as negative. Following Liublinska and Rubin (2014), a graphical display (heat map) is used to indicate the tipping point analysis results for each combination of imputed missing values. The risk difference in TEAR rate across the treatment arms is presented for each combination in the heat map. The graph will display the sensitivity across the range of missing values as a color gradient from most favorable for the test treatment arm to the most favorable for the reference treatment.

In addition, the TEAR rate at each scheduled visit (visitwise TEAR [vTEAR]) will be summarized at each scheduled visit by using the following criteria: Subjects who are ADA negative at baseline and become positive at a specific visit (Treatment Induced TEAR), and subjects who are ADA positive at baseline and obtain a 4-fold increase in titer at a specific visit (Treatment Boosted TEAR), will each be counted as TEAR positive at the specified visit.

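### SAP 8.7.2.1 closes with an equivalence rule opposite to the one it opens with, and the sample tipping-point flag in SAP 10.2 stars almost every cell

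*SAP*

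**What the plan says.** **Primary rule.** In SAP 8.7.2.1, "The null hypothesis is non-equivalence, expressed by" an absolute difference in true TEAR rates of at least δ. The decision follows: "The null will be rejected in favor of equivalence if the 90% confidence interval of the treatment difference is within the range" (−δ, δ). SAP 8.7.1 agrees, requiring that the interval "is within the pre-specified margin as displayed in Table 2 of the study SAP". So does protocol 7.2.3: "Equivalence of TEAR rate will be established if 90% confidence interval of treatment difference" lies within the ± margin of its Table 5. Protocol 7.2.2 says the same.

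SAP 8.7.2.1 then restates the rule in two other ways. One rejects the null if neither −δ nor δ "is contained within the 90% confidence interval". The other follows the margin formula, which is introduced with "Under the null hypothesis of equivalence" (pM = pN), and reads: "If the margin falls within the 90% confidence interval for the risk difference, then equivalence of MYL1601-D and Novolog will be declared".

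**Tipping point.** SAP 8.7.2.3 looks for the point at which "the equivalence boundary is crossed and the results fail to reject non-equivalence", but the condition it displays compares the estimated difference with δ. The text of SAP 10.2 also stars a cell when the point estimate is outside the margin. The sample code in 10.2 does something else: it leaves the asterisk blank only if +margin and −margin both lie strictly inside the 90% limits, and stars every other cell.

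**The concern.** An interval strictly inside (−δ, δ) contains neither limit, so the opening and closing rules of 8.7.2.1 cannot both be met. The section also names opposite null hypotheses. Its middle restatement is too loose, because an interval lying wholly beyond δ contains neither limit either.

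The heat map is a named sensitivity analysis of the primary endpoint. It should show which assumptions about missing TEAR status would lose equivalence. If the star is set by the sample code, it cannot. If it is set by the text, some scenarios are shown as passing although the primary rule fails them.

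Three smaller inconsistencies touch the same test:

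- **Margin quantile.** The formula prints z_β, while the 10.2 code uses the 0.90 quantile, which is z_(β/2) at 80% power.
- **n in the margin.** Table 2 is built on 250, the 10.2 code uses the number randomized, and 8.7.2.1 does not define n_N. The ITT set meanwhile leaves out site 6103.
- **Pooled interval.** The 8.7.2.1 text uses a t quantile and its code uses 1.645. In 10.1.3 the step that prints the pooled limits sets no confidence level.

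**Working it through.** **Inputs.** 250 per arm and two one-sided tests at 0.05 (SAP 5); 90% Wald limits with 1.645 (code in SAP 8.7.2.1); margin quantiles 0.95 and 0.90 (code in SAP 10.2).

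**1. The plan's own margins.** δ = (z_0.95 + z_0.90) × √(2p(1−p)/250), with z_0.95 + z_0.90 = 2.926, reproduces all 12 rows of Table 2. At p = 20%: 2.926 × √(2 × 0.2 × 0.8/250) = 2.926 × 0.03578 = 10.47% (table 10.5%). Reading z_β as the 0.80 quantile gives a sum of 2.486 and margins of 4.85%, 10.19% and 11.12% at 5%, 30% and 50%, against 5.7%, 12.0% and 13.1% in the table. n = 245 gives 5.76% at 5% (table 5.7%) and n = 255 gives 7.78% at 10% (table 7.9%), so the table implies 250.

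**2. The three wordings on the same data.** NovoLog 50/250, δ = 10.47%. The closing sentence is read with the margin as +δ.

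| MYL-1601D | Difference | SE | 90% CI | CI inside ±δ | Neither limit in CI | Margin in CI |
|---|---|---|---|---|---|---|
| 50/250 | 0.0% | 3.58% | −5.9% to 5.9% | equivalent | equivalent | not |
| 76/250 | 10.4% | 3.86% | 4.1% to 16.7% | not | not | equivalent |
| 100/250 | 20.0% | 4.00% | 13.4% to 26.6% | not | equivalent | not |

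**3. Operating characteristics.** These are exact binomial sums over all outcomes, at reference rates of 5% to 50%. With the CI inside the margin, equivalence is declared with probability 79.5% to 80.5% at zero difference and 4.9% to 8.8% at a true difference of δ. The closing sentence taken literally gives 9.7% to 16.2% and 82.1% to 89.9%.

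**4. The coded flag.** I applied it to all 251 × 251 = 63,001 count pairs:

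- 5,693 meet equivalence, and all of them are starred.
- Of the other 57,308, 57,304 are starred too.
- The 4 unstarred pairs have NovoLog at 0/250 (MYL-1601D 1 or 2) or 250/250 (MYL-1601D 248 or 249).

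The reason is simple. The CI can hold both limits only if its half-width, 1.645 SE, exceeds δ. With similar rates in the two arms δ is about 2.926 SE, so this can happen only when the reference rate is essentially 0 or 1.

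**5. The text criterion.** At NovoLog 50/250 the CI rule is met for 38 to 60 MYL-1601D TEAR subjects, and the point-estimate criterion for 24 to 76. The table counts heat-map cells that pass on the point estimate but fail the CI rule. The missing counts and the observed positives are assumptions; denominators are 250.

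| Missing per arm | Cells in map | 50 v 50 observed | 58 (MYL-1601D) v 50 observed |
|---|---|---|---|
| 5 | 36 | 0 | 4 |
| 12 | 169 | 2 | 46 |
| 25 | 676 | 184 | 230 |
| 38 | 1,521 | 584 | 569 |

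The coded flag leaves no cell unstarred in any of these eight maps.

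**6. The smaller items.**

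- The t quantile on 498 df is 1.648; with it 5,685 pairs meet equivalence instead of 5,693, and the 38 to 60 range is unchanged.
- At a 20% rate the margin is 10.69%, 10.47% and 10.27% for n = 240, 250 and 260 (240 and 260 are assumed).
- If the 10.1.3 limits came out at 95% (an assumption), power with equal arms at 10%, 20% and 30% would be 66.7%, 66.4% and 66.8%, against 80.0%, 79.7% and 79.6% with 1.645. The range at 50/250 would narrow to 41 to 58.

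**The case against.** The strongest reply is that nobody would be misled about the primary rule. The CI-inside-margin form stands in several places in both documents, and the reversed sentence stands alone. The loose restatement follows directly on the exact rule. This is right, and it is why the point is a correction and not a threat to the primary result.

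The 10.2 code is offered only as a model. Its merge by x and y would need a sort first, so someone must revise it anyway. Each cell also prints the risk difference and carries a colour, so the map is not empty even if the star is. That holds, but the text tells the programmer that the asterisk variable was created in the sample code for this very purpose, and neither number nor colour shows whether the CI rule is met.

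SAP 8.7.2.3 speaks of failing to reject non-equivalence, which suggests a CI criterion. Its displayed condition is nevertheless on the point estimate, and so is the 10.2 text.

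On the smaller items, SAP 8.7.1 refers to the Section 10 code for the margin, which largely settles the quantile. The t quantile is negligible. The power loss depends on 10.1.3 giving 95% limits, while the plan elsewhere specifies 90%. These are points of consistency.

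The counts depend slightly on rounding: with the exact normal quantile 5,695 pairs meet equivalence, and the last table entry is 568. No conclusion changes.

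**Conclusion.** The concern holds. SAP 8.7.2.1 ends with a decision rule that reverses its own opening rule, SAP 8.7.1 and protocol 7.2.2 and 7.2.3. The primary verdict would probably survive, because the correct rule is clear elsewhere. The tipping-point flag as coded is uninformative: 4 of 63,001 pairs are unstarred, and none of those meets equivalence. This rests only on 250 per arm and the SAP's own formulas. The text criterion is more lenient than the primary rule (24 to 76 against 38 to 60 at NovoLog 50/250). How many cells that affects depends on the amount of missing data, which the documents do not give; it is none or few at 5 missing per arm and several hundred at 38. This should be fixed.

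**What to change.** 1. In SAP 8.7.2.1 give one rule in place of the three wordings: equivalence is declared if the lower 90% limit is above −δ and the upper 90% limit is below +δ. Describe pM = pN as the assumption used to derive the margin, not as a null hypothesis.
2. In SAP 10.2 set the flag with `if lowercl > -margin and uppercl < margin then asterisk=' '; else asterisk='*';`. State the same CI criterion in the text of 8.7.2.3 and 10.2. Sort HEATMAP by x and y before the merge, because its loops write it in y-then-x order.
3. Print the margin formula with z_(β/2), and use one n in 8.7.2.1, Table 2 and 10.2. Keeping 250 leaves Table 2 and protocol Table 5 as they are; another n requires changing both tables.
4. Use one pooled 90% interval throughout. Replace the 10.1.3 output that sets no level, and choose between the t quantile and 1.645.

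The cost is SAP wording and a few lines of sample code. No data collection or patient burden is involved.
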